4. **Briefly** describe the research/evaluative study design. *(Use charts and flow diagrams if applicable. "See protocol" is not an acceptable response.)*

a. Subjects: State inclusion and exclusion criteria.

Preliminary Focus Group Participants (2 groups, each group n=10):

- Male or Female
- Self-identifies as being Hispanic or Latino
- 50 to 75 years of age
- Patients in the Lehigh Valley Health Network

Patient and Stakeholder Advisory Committee Members (n=12):

Patient Members, Inclusion Criteria:

- Male or Female
- Self-identifies as being Hispanic or Latino
- 50 to 75 years of age

Stakeholder Members, Inclusion Criteria:

- Male or Female
- Stakeholders in the Hispanic community or the Lehigh Valley Health Network

Study Subjects (n=400):

Inclusion Criteria

- Male or Female
- Self-identifies as being Hispanic or Latino
- 50 to 75 years of age
- Patients in the Lehigh Valley Health System

Exclusion Criteria

- Previous diagnosis of CRC
- Up to date with CRC screening guidelines.
- Family history of CRC diagnosed before the age of 60 years

Follow-up Focus Groups (2 groups, each group n=10):

- Previously enrolled study subjects

Evaluation

- Interviews: ≤14 interviews of research team members and practice administration as related to intervention implementation

- b. Procedures: Explain study procedures/methods.

Preliminary Focus Groups:

During the first six months of the proposed study, we will work with the Fox Chase Cancer Center Office of Health Communications & Health Disparities (OHCHD) to develop study materials and conduct two focus groups with Hispanic patients from LVHN primary care practices. The OHCHD has 30 years of experience communicating and disseminating current, evidence-based, culturally-appropriate cancer information. OHCHD staff members have expertise in health communications and cancer control, and bi-lingual, bi-cultural staff members have extensive experience in developing programs for racial and ethnic minorities and in conducting focus groups in Spanish.

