Participant Recruitment, Baseline Survey Administration, and Randomization. Initially, Hispanic patients who are 50 to 75 years of age, have not been diagnosed with CRC, and have not had a recent CRC screening test will be identified via LVHN electronic records. These individuals will be mailed a study invitation letter in English and Spanish. The letter will describe the proposed research and provide information about ways to opt out of or register to participate in the study (i.e., complete and return a study registration card in an addressed postage-paid return envelope, or call a toll-free telephone number.) The letter will also inform recipients that a research staff member will call non-respondents.

A trained bilingual research assistant will call patients within 15 days after the invitation letter mailing. The research assistant will conduct the call in the language preferred by the respondent. The research assistant will verify patient eligibility, describe the study, ascertain patient willingness to participate, obtain verbal consent, and administer a brief baseline survey to a total

of 400 participants. As part of the survey, the research assistant will describe SBT and colonoscopy screening, and will ascertain the participant’s overall and test-specific screening decision stage. We will use this information to determine the participant’s overall CRC screening decision stage and preferred CRC screening test. Data on sociodemographic background will also be collected. At the end of the baseline survey, the interviewer will ask participants to indicate a day(s) of the week and time(s) of the day when research staff can most conveniently speak to the participant by telephone. The interviewer will also ask for a telephone number and email address for use in making contact. Finally, the research assistant will inform the participants that they will receive CRC screening materials in the mail, will determine whether the participant wants to receive study materials in English or Spanish, and will mention that the research team may contact them by telephone to discuss screening and will contact them to complete two follow-up surveys. As shown in **Figure 1**, research staff will randomly assign all consented participants either to a SI Group or a DSNI Group. Random assignment will be stratified by participant primary care practice.

Figure 1. Study Design					

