mailed print materials, including a letter from the practice on CRC screening, an informational booklet, and instructions for arranging a colonoscopy appointment and instructions for completing an enclosed immunochemical SBT kit. Again, print materials will be provided in the language specified by the participant at baseline. Within 7 days after this mailing, DSNI Group participants will also receive a telephone call from a trained bilingual study navigator. In the call, the navigator initially will review the CRC screening materials and verify the participant's preferred CRC screening test. During this encounter, the navigator will also use an online Decision Counseling Program[©] (DCP) to identify barriers to and facilitators of preferred test performance, determine the likelihood of test performance, and develop a personal screening plan.

The online DCP includes a script that guides the navigator and participant through a structured telephone encounter with participants. Following the script, the navigator will elicit major factors that would influence the participant to or not to (pros and cons) screen, determine the level of importance the patient assigns to each factor (not important to overwhelmingly important), enter the reported factors and factor weights into the DCP, and compute a screening likelihood score (low to high). The navigator will then review the result with the patient, and will use a Motivational Interviewing approach to develop a plan to reinforce facilitators and overcome barriers to performing the individual's preferred test. For participants who prefer colonoscopy screening, the navigator will be authorized to obtain appropriate referral approvals, and will help to schedule a colonoscopy appointment at the time of the navigation call. For those who prefer SBT screening, the navigator will explain steps for performing the test, and offer to be available to answer questions that arise about SBT completion. For colonoscopy and SBT screening, the navigator will follow up with the participant to address emergent questions or concerns.

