Aim 4 (DSNI versus SI on CRC and screening knowledge and perceptions). Knowledge and perceptions (PHM scales) about CRC and screening will be assessed at the 6-month survey. We hypothesize that DSNI Group participants will have higher knowledge and more favorable perceptions than SI Group participants. The analyses of knowledge and perception scales will be based on linear regression. However, if some of the scales are skewed, some transformation will be needed prior to the analyses (e.g., log). Alternatively, some of the outcomes might be used as dichotomous or categorical, in which case the analyses will rely on logistic regression. The analysis strategy will be similar to that for Aim 2 (i.e., control for practice, as well as all participant baseline characteristics).

Additional Analyses. Data on tailored navigation and support delivery (e.g., number and timing of navigator call attempts, time from randomization to initiation and completion of contact, validation of test preference, assessment of screening likelihood, reasons for incomplete delivery of the navigation call, and mailing of the screening plan and screening status report) will also be collected and summarized. We will also assess the potential interaction between study group and sex and age, by the addition of corresponding interaction terms to the main logistic regression

model of Aim 1. Using electronic medical records data for SBT screenees, we will also describe patterns of screening beyond the initial 12-month observation period for SBT-negative patients and patterns of diagnostic follow-up for SBT-positive patients.

Sample Size and Power. As shown in Figure 1 above, we will randomize 400 LVHN Hispanic patients (200 per study group). We expect to have CRC screening data for at least 95% of the participants, given access to patient electronic medical records, and direct reports from a centralized SBT laboratory (N~380). Given our prior experience in similar research studies, we also expect an 80% completion rate for the endpoint survey (N~320).

Power for Aim 1. Based on our previous research and given the planned enhancements in the decision support and navigation intervention, we expect overall CRC screening rates to be about 30% in the SI Group and at least 45% in the DSNI Group (odds ratio, OR = 1.9). Given a projected total sample size of 380 and a two-sided alpha of 0.05, the study has 85% power for Aim 1.

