The PASAC committee will review surveys so that the questions are relevant to patients. In addition, data will be double-entered and verified in the database in order to assure accuracy. Finally, all analyses will be done by or with the assistance of biostatisticians so that results and conclusions are accurate.

7. Identify the sources of data obtained about human subjects in the form of specimens, records, survey instruments, interviews, focus groups, observation, or other sources.

Data Type	Data Elements	Data Source
Demographic data	Name, telephone number(s), mailing address, insurance status	LVHN IDX administrative database
Demographic data	Age, ethnicity, race, education, income and marital status. E-mail address and cell telephone number. Language preference.	Baseline survey
Medical Records data	Colorectal cancer related screening and diagnostic history	LVHN IDX administrative database
Data collected for the study	Decision stage related to screening SBT and colonoscopy	Baseline & 6-month survey
	Decision factors, factor weights, screening likelihood score	Decision counseling session (DSNI Group only)
	Factors that influence screening, barriers to screen and steps in the screening plan.	Navigation log
	SBT (FIT or some other SBT) and colonoscopy screening use. Flexible sigmoidoscopy and barium enema x-ray use. Test-specific decision stage, acculturation, fatalism, and perceptions regarding CRC screening and CRC screening knowledge	6-month survey
	SBT(FIT or some other SBT) and colonoscopy Screening use. Flexible sigmoidoscopy and barium enema x-ray use.	6- and 12-month medical records review/EMR

8. Please check off those steps noted below that you intend to implement to ensure confidentiality of Subject data and to protect the identifiers or codes that can be linked to identifiers from improper use or disclosure. (Note: Non-Jefferson sanctioned “covered devices” may **not** be used for the storage of identifiable Subject data. See **Jefferson Policy #122.35, “Wireless and Portable Device Security Policy.”**)

- List of identifiers will be kept in a separate location from the coded Subject data that can be linked to identifiers.
- Subject data will be kept in a locked filing cabinet or desk and in a locked office.
- Subject data will be kept on a password-protected, encrypted on-site computer.
- Subject data will be kept on a Jefferson server. Provide specific physical and/or electronic location:

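### Entry is not limited to one person per household, so eligible housemates may be randomised to opposite arms and the SI member may be partly exposed to navigation.

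*Combined protocol and SAP*

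**What the plan says.** Part A, item 4a admits men and women who identify as Hispanic or Latino, are aged 50 to 75, and meet the criterion "Patients in the Lehigh Valley Health System". Its three exclusions are a previous CRC diagnosis, being up to date with screening, and a family history of early CRC. None refers to the household.

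Item 4b (Participant Recruitment, Baseline Survey Administration, and Randomization) draws candidates from LVHN electronic records, invites them by mail, checks eligibility by telephone, and randomises everyone who consents. The only allocation constraint is this: "Random assignment will be stratified by participant primary care practice".

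In item 4b (Intervention Implementation) the arms differ in navigation: "DSNI Group participants will also receive a telephone call from a trained bilingual study navigator". The navigator reviews the materials, discusses barriers and facilitators, explains the steps of the stool blood test (SBT) or helps to schedule a colonoscopy, follows up on questions, and sends the participant a one-page summary with a screening plan. Figure 1 lists the same mailed contacts for both arms.

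The Aim 1 model in item 4c adjusts for practice, gender and age, plus any variable with substantial baseline imbalance. Neither the analysis nor the power section mentions households or contamination between arms. The item 7 table shows that the LVHN administrative database holds "Name, telephone number(s), mailing address, insurance status".

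**The concern.** Spouses, siblings or other relatives in this age band who live together can each meet every criterion. Stratifying by practice balances the arms within a practice but does not keep housemates in the same arm.

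Where a pair is split, the SI member lives with someone who is counselled by telephone and receives a written plan. That SI member already has the same SBT kit and colonoscopy instructions, so an explanation given to one person can be used by the other. Decision stage (Aim 2) and knowledge and perceptions (Aim 4) could also shift through conversation at home.

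Any such sharing raises SI outcomes and shrinks the contrast. Intent-to-treat analysis and baseline adjustment do not restore it, and the power statements make no allowance for it. The bias runs against the trial's own hypothesis, so the risk is a missed or understated effect.

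**Working it through.** **Inputs from the plan (item 4c, Sample Size and Power).**
- Size: "we will randomize 400 LVHN Hispanic patients (200 per study group"), and "We expect to have CRC screening data for at least 95% of the participants", which gives 380 analysed, or 190 per arm.
- Aim 1 rates: "about 30% in the SI Group and at least 45% in the DSNI Group (odds ratio, OR = 1.9").
- Aim 1 power: "Given a projected total sample size of 380 and a two-sided alpha of 0.05, the study has 85% power for Aim 1".
- Aim 2: 35% versus 51%, about 320 analysed (160 per arm), stated power 82%.

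**Formula.** Two-proportion normal approximation: power = Φ[(d − 1.96·s0)/s1]. Here d is the difference, s0 = √(2·p̄(1−p̄)/n), and s1 = √((p1(1−p1) + p2(1−p2))/n).

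**Reproducing the plan's figures.**
- Aim 1: p̄ = 0.375, s0 = √(2 × 0.375 × 0.625/190) = 0.0497, s1 = √((0.21 + 0.2475)/190) = 0.0491. Power = Φ[(0.15 − 1.96 × 0.0497)/0.0491] = 85.8%, against 85% stated.
- Aim 2: the same formula with n = 160 gives 82.7%, against 82% stated.

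Both stated figures stand.

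**Assumptions that the documents do not supply.**
- h: share of participants who live with another participant, taken as 10%, 20% or 30%.
- Split: under independent 1:1 assignment about half of pairs are split, so the exposed share of SI is f = h/2. Block size is not given, and small blocks could raise this share for people enrolled one after the other.
- c: share of the planned difference that carries over to an exposed SI participant, taken as 0.5, with 1 as the upper bound.

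The SI rate becomes p1 + f·c·(p2 − p1), and the DSNI rate is unchanged.

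In people, h = 10% of 400 is 40 participants in 20 pairs. About 10 pairs are split, so about 10 of 200 SI participants (5%) are exposed.

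**Worked case, Aim 1, h = 10%, c = 0.5.** SI rate = 0.30 + 0.05 × 0.5 × 0.15 = 0.30375, so d = 0.14625 and power = 84.0%.

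| h | f | Aim 1 difference, c = 0.5 (points) | Aim 1 power, c = 0.5 | Aim 1 power, c = 1 | Aim 2 power, c = 0.5 |
|---|---|---|---|---|---|
| 0% | 0% | 15.0 | 85.8% | 85.8% | 82.7% |
| 10% | 5% | 14.6 | 84.0% | 81.9% | 80.7% |
| 20% | 10% | 14.25 | 81.9% | 77.5% | 78.6% |
| 30% | 15% | 13.9 | 79.8% | 72.5% | 76.3% |

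Aims 3 and 4 were not quantified. The direction of the bias is the same.

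**The case against.** **Nothing says that pairs exist.** The documents do not report that couples are expected or that they share a telephone or a practice. Contact details are collected per participant. A 30% share would mean 60 pairs among 400 participants (0.30 × 400 / 2), with both members eligible, reached and consenting. This stands: the frequency is unknown, and the lower rows of the table may never arise.

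**Much of navigation is personal.** The factor weights, likelihood score, referral, appointment and chart entry belong to one participant and do nothing for a housemate. Navigation is expected to reach only about 85% of the DSNI arm. A reader might infer that the SI member of a split pair simply receives the intervention. The documents do not support that. They support possible partial exposure, through advice passed on and the mailed plan, so full carry-over is a ceiling.

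**Correlated outcomes.** A reader might also infer that the logistic model is invalid because housemates' outcomes are related. Under individual randomisation, same-arm pairs raise the variance of the difference and split pairs lower it, and the two roughly cancel. In simulations with no true effect, 30% of participants paired and within-pair correlation 0.5, an ordinary two-proportion test rejected 5.05% to 5.2% of the time at nominal 5%. This gives no ground for criticising the planned test.

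**Silence in a summary form.** The form asks for a succinct synopsis and cites a Section 3.3.2 that is not in the supplied text, so a household rule might exist elsewhere. That is possible. But item 4a lists the criteria and item 4b describes the draw and the allocation, and a rule would belong in one of them.

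**Pool size.** Part B, item 2 answers YES to having enough potential subjects, but under the current criteria. The point has some force: the more common pairs are, the more a household rule costs. It does not remove the route for contamination.

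**Conclusion.** The gap is real and its likely effect is modest. Nothing in the supplied text stops housemates from entering and being split between arms, and any sharing would pull the result toward no difference.

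The size cannot be fixed from the documents. At 10% pairing and half carry-over, Aim 1 loses under 2 points of power (85.8% to 84.0%). At 30% pairing it reaches 79.8%. Aim 2, the other primary objective, starts lower and drops below 80% at 20% pairing (78.6%). These figures rest entirely on the assumed pairing, the assumed carry-over and an even chance of a split.

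The plan's power statements are not in error. The recommendation is an inexpensive safeguard, best applied before randomisation because contamination cannot be undone afterwards.

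**What to change.** Add to the study-subject criteria in Part A, item 4a: *Only one participant per household.* Then describe how it is applied in item 4b:
- match mailing address and telephone number in the LVHN draw;
- send the invitation to one randomly chosen eligible person per address;
- have the research assistant confirm, on the existing eligibility call, that nobody else in the household is enrolled;
- if the chosen person declines or is ineligible, allow another eligible member of that household to be invited.

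The cost is one matching step on data already held and one extra question on a call already planned. The downside is a somewhat smaller invitation pool. The replacement rule limits this, because a household is not lost when its first invitee does not enrol. The sponsor should count shared addresses in the draw before adopting the rule. That count shows both how much exposure is avoided and how many invitations are given up.

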Baseline Survey	Randomization	Intervention Delivery		Records Review (6,12 month)	6-Month Survey
Complete (N = 400)	Stratify random assignment by primary practice	Standard Intervention (SI) (n = 200)	Mailed contacts*	Complete (n = 190)	Complete (n = 160)
		Decision Support and Navigation Intervention (DSNI) (n = 200)	Mailed contacts, Support/Navigation contacts**	Complete (n = 190)	Complete (n = 160)
* Mailed Contacts: Screening letter, informational booklet, colonoscopy instructions, SBT kit, and reminder letter.					
**Mailed Contacts: Screening letter, informational booklet, colonoscopy instructions, SBT kit, and reminder letter; Support/Navigation contacts: navigator calls to provide decision counseling, develop screening plans, support plan implementation, and deliver screening plan and status reports.					

Intervention Implementation. Following randomization, **SI Group** participants will be mailed a set of standard materials. The materials will include a letter from the participant’s primary care practice encouraging selection and performance of either (1) colonoscopy screening, or (2) stool blood test (SBT). Accompanying the letter will be instructions for arranging a colonoscopy appointment and instructions for completing an enclosed immunochemical SBT kit. Print materials and contacts will be provided in the language the participant as preferred (English or Spanish) at the time of the baseline survey. At 45 days following random assignment, research staff will send participants a reminder letter from the participant’s primary care provider that endorses and encourages screening. Study participants assigned to the **DSNI Group** will also be

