CRC screening, the report will advise providers and the office manager to contact the participant and encourage screening. For those screenees who require follow-up of an abnormal SBT result, the report will also encourage providers to arrange a diagnostic colonoscopy. For patients who had a normal SBT result, the report will encourage providers to contact patients in a year to offer screening. Finally, 30 days after the screening status report is mailed, the navigator will contact the office manager to verify provider receipt of the screening status report and to record follow-up action(s) taken.

Six-Month Survey and Medical Records Review. Six months after randomization, a survey interviewer from Survey Technology and Research (STR), a professional survey company, will contact each participant by telephone and administer a 6-month Survey. The survey will include items that assess participant sociodemographic characteristics. In addition, items will be included on the survey to assess CRC screening decision stage and screening test preference. In terms of actual screening adherence, survey respondents will also be asked to report any CRC screening tests performed during the 6 months. For all reported tests, participants will be asked to provide a date of testing. Following prior studies, we will allow for 20% missing survey data.

A 6-month medical records review for DSNI Group participants will be completed by a study research assistant. Screening adherence data collected on the 6-month survey and 6-month medical records review will be used to prepare the DSNI Group screening status report described earlier, and to assess the CRC screening outcome. Participant insurance status will also be ascertained on medical records review. CRC screening adherence will reflect performance of any ACS or USPSTF guidelines-recommended CRC screening test recorded in the chart or self-reported on the survey, if the survey report is accompanied by a procedure date that falls within the 6-month study period following randomization.

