Twelve-Month Medical Records Review. At 12 months after randomization, an endpoint medical records review will be performed on all study participants to assess CRC screening adherence. The medical records review will be conducted by a study research assistant who will be blinded to each participant's study group assignment. Any ACS or USPSTF guidelines-recommended CRC screening test will be accepted. Following prior studies, we will allow for 5% missing endpoint medical records data. As part of the records review, we will review electronic medical records for all participants in the last year of the study to characterize patterns of screening use among participants after the study observation period. This information will be combined with self-reported CRC screening from the 6-month survey and 6-month medical records review to determine the main study outcome in the analyses.

Follow-up Focus Groups:

In the last year of the study, the research team will also work with the OHCHD to conduct two focus groups with DSNI Group participants. The two focus groups will include screenees (n=10) and nonscreeners (n=10). We will develop discussion guides for use in eliciting participant perceptions about intervention contacts, and barriers to and facilitators of screening. Focus groups will be conducted in Spanish or English, as needed, and will be audio recorded.

Evaluation:

The research team will apply the Reach, Effectiveness, Adoption, Implementation, and Maintenance (RE-AIM) framework. We will complete an assessment of RE-AIM dimensions at different levels of the LVHN for the interim and final reports to the sponsor.

c. Data analysis: Provide the methods by which the study objectives/aims will be assessed or measured, i.e., statistical analysis plan, qualitative research methods such as procedures for conducting theme analysis and enhancing validity, program evaluation methods and analysis plan, or mixed methods analysis plan. For a quantitative study include what statistical tools will be applied and how the study is powered, if appropriate. Pilot studies do not require a statistical plan.

Preliminary Focus Groups

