Aim 1 (DSNI versus SI on overall CRC screening adherence). The two study groups will be compared in terms of the fraction of participants who undergo CRC screening (through SBT, colonoscopy, flexible sigmoidoscopy, etc.) within 12 months of the randomization date. Screening status will be determined using both the 6-month survey and 12-month medical records review data. We hypothesize that DSNI Group participants will have higher overall screening than SI Group participants. We will analyze screening (yes vs. no) via logistic regression, using study group (DSNI versus SI) as the main predictor. As mentioned above, we expect the two study groups to be comparable at baseline due to randomization. So, the model will control only for practice and participant gender and age (the latter two variables will be included to allow addition of interaction between study group and gender or age in secondary analyses). If, however, substantial baseline imbalances occur, the model will include for those additional variables.

Aim 2 (DSNI versus SI on change in CRC screening decision stage). CRC screening decision stage will be assessed in both the baseline and 6-month surveys. Forward change (between baseline and endpoint) will encompass any movement from a lower to a higher decision stage. We hypothesize that DSNI Group participants will have greater forward movement in screening decision stage than SI Group participants. We will analyze forward change in screening decision stage (yes vs. no) via logistic regression. These analyses will be based on 6-month survey data. Prior research suggests that survey response will be comparable in both study groups. The model will include practice and participant baseline characteristics.

Aim 3 (DSNI versus SI on test-specific CRC screening adherence). The two study groups will be compared in terms of the fraction of participants who undergo a SBT or a colonoscopy within 12 months. Due to current screening practices in primary care, we expect very few, if any, instances of screening via other modalities. We hypothesize that DSNI Group participants will have higher SBT and colonoscopy screening than SI Group participants. The main analysis of test-specific screening (no screening, SBT screening, colonoscopy screening) will be based on polytomous (multinomial) logistic regression. The analysis strategy will be similar to that for Aim 1 (i.e., control for practice, as well as participant gender and age).

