to obtain data to measure this dimension. We will measure intervention **efficacy/effectiveness** at the patient level in terms of impact on defined primary outcomes (i.e., screening adherence, screening decision stage, and test-specific adherence). Here, we will use data from the 6-month survey, 6-month medical records review, and 12-month medical records review to evaluate this dimension. In terms of intervention **adoption**, we will determine the number and percentage of providers and office managers who acknowledge receipt of screening plans and reports by study navigators and provide feedback on provider review of this documentation. We will assess intervention **implementation** by determining the number and timing of attempted and completed navigator calls, time from call initiation to call completion, length of calls, and reasons for incomplete calls. We will also track navigator contacts with provider practices in a similar manner. In addition, qualitative data will be collected from the navigators about their experience implementing the intervention: what worked well and what didn't, whether patients utilized their assistance, and what were the key services that they offered that they believe contributed to completion of screening. We will also interview selected lead physicians and office managers from participating practices in order to obtain information on their experience receiving and acting on intervention-related contacts, including feedback from patients, study navigator contacts, and their receipt of participant screening plans and reports.

5. Delineate procedures that are standard of care from those that are being performed specifically for the research.

There are national guidelines for CRC screening, but how they are implemented in specific practices with specific patients varies widely. At this time, in most primary care practices, systematic approaches to screening recommendations and follow-up are not being implemented. Throughout the course of this study participants may receive mailed educational materials, an SBT kit and a call from a trained patient navigator in order to encourage screening.

6. How will accuracy of data be assessed?

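### The sources for the main screening outcome conflict, and one reading gives the DSNI arm a records review that the SI arm does not get

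*Combined protocol and SAP*

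**What the plan says.** All references are to the combined protocol and SAP, Part A.

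- **4b, Six-Month Survey and Medical Records Review.** "A 6-month medical records review for DSNI Group participants will be completed by a study research assistant". With the 6-month survey, its data serve the "DSNI Group screening status report described earlier, and to assess the CRC screening outcome". Nothing is said about blinding. The survey itself goes to each participant.
- **4b, Twelve-Month Medical Records Review.** This review covers all participants, and the reviewer is blinded to group. The paragraph then mentions a last-year look at electronic records "to characterize patterns of screening use among participants after the study observation period". The next sentence says that this information will be combined with self-reports from the "6-month survey and 6-month medical records review to determine the main study outcome in the analyses".
- **4c, Aim 1.** The outcome is screening within 12 months of randomization. "Screening status will be determined using both the 6-month survey and 12-month medical records review data". The 6-month records review is not named.
- **Figure 1.** The records-review column is headed with both 6 and 12 months and shows 190 complete in each arm.
- **Item 7, data-source table.** The row reads "6- and 12-month medical records review/EMR" and carries no arm limit, although the decision-counseling row is marked as DSNI only.
- **4c, Evaluation (RE-AIM).** Effectiveness will use the 6-month survey, "6-month medical records review, and 12-month medical records review to evaluate this dimension", again with no arm limit.

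**The concern.** Two things are left open: whether SI participants get a 6-month records review, and whether that review feeds the Aim 1 outcome. Two analysts working from this document could build different primary variables.

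If the two procedures paragraphs are followed as written, DSNI has three sources for the outcome and SI has two. An extra source in one arm can only add screened participants to that arm. A reviewer who looks only at DSNI charts also knows the arm. Adjusting for practice, age and gender does not remove a difference in how the outcome is found.

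Aim 3 counts the same tests over the same 12 months and states no sources of its own, so it probably shares the problem.

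There is a second ambiguity. In the twelve-month paragraph, the words introducing the combined sources directly follow the sentence on screening after the observation period. Read literally, later data would enter an outcome that Aim 1 limits to 12 months.

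**Working it through.** **The plan's own figure.** Aim 1 assumes 30% versus 45%, 190 analysed per arm, two-sided alpha 0.05. With the pooled two-proportion test:

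(0.15 − 1.96 × √(2 × 0.375 × 0.625/190)) / √((0.30 × 0.70 + 0.45 × 0.55)/190) = (0.15 − 0.0974)/0.0491 = 1.07, so power is 85.8%.

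The plan states 85%, so the figure reproduces and is not in dispute.

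**Size of a one-arm source.** The documents give no capture rates, so these are assumptions:

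- true screening p = 35% in both arms, with no true effect;
- sensitivity of one chart pass s = 85 to 95%;
- share of tests in months 0 to 6, f = 60 to 100%;
- share of those that the survey catches independently, v = 50 to 80% (the plan expects 80% survey response);
- recovery factor r for the extra pass: 1 if the passes are independent, 0.5 if it recovers half as much because both read the same record.

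Observed SI rate = p × [f × (1 − (1 − s)(1 − v)) + (1 − f) × s].

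*Route 1: the extra pass finds tests that the 12-month pass missed (190 per arm).* False uplift = p × f × (1 − s) × (1 − v) × r × s.

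- Largest: 0.35 × 1 × 0.15 × 0.5 × 1 × 0.85 = 2.23 points.
- Smallest with r = 1: 0.35 × 0.6 × 0.05 × 0.2 × 1 × 0.95 = 0.20 points.

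| s | Uplift, r = 1 | Uplift, r = 0.5 |
|---|---|---|
| 85% | 0.5–2.2 points | 0.3–1.1 points |
| 90% | 0.4–1.6 points | 0.2–0.8 points |
| 95% | 0.2–0.8 points | 0.1–0.4 points |

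Type I error is at most 7.5% with r = 1 and 5.6% with r = 0.5.

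*Route 2: the 12-month record is missing (the plan allows 5%) and counts as not screened unless another source is positive (200 per arm).* False uplift = 0.05 × p × f × (1 − v) × s.

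- Largest: 0.05 × 0.35 × 1 × 0.5 × 0.95 = 0.83 points.
- Smallest: 0.05 × 0.35 × 0.6 × 0.2 × 0.85 = 0.18 points.
- Type I error is at most 5.4%.
- If missing records are instead excluded unless another source is positive, the uplift is 0.12–0.56 points and type I error at most 5.15%.
- If the survey caught none of these tests (v = 0), the uplift with missing counted as not screened would be 0.9–1.7 points and type I error 5.4–6.5%.

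*Both routes, survey included (200 per arm).* Uplift = 0.95 × route 1 + route 2. Largest: 0.95 × 2.23 + 0.05 × 0.35 × 0.5 × 0.85 × 100 = 2.12 + 0.74 = 2.86 points.

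| Recovery | Uplift | Highest type I error |
|---|---|---|
| r = 1 | 0.4–2.9 points | 9.3% |
| r = 0.5 | 0.3–1.8 points | 6.7% |
| r = 0 | 0.2–0.8 points (route 2 alone) | 5.4% |

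With the Aim 1 sources in both arms, the review adds no uplift and the nominal 5% is kept.

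**The case against.** The strongest reply is that the analysis text is already symmetric. Aim 1 names two sources that cover everyone, one of them blinded, and an analyst who follows it meets no asymmetry from the review. The procedures text says the 6-month review is for DSNI participants but does not expressly exclude SI, and three other places show no arm limit. Both points stand. They show that a harmless reading exists, not that the plan settles on it: the twelve-month paragraph still puts the review into the main outcome.

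The arithmetic can also be challenged, with some force.

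- A test never entered in the record cannot be found by a second pass through it. If unrecorded tests make up the whole shortfall, r is near 0 and route 1 vanishes.
- The plan expects direct reports from a central stool-test laboratory, which also points low.
- The planned SI rate is 30%, not 35%. At 30% the combined maxima fall to 2.45 points and 8.5% (r = 1), or 1.55 points and 6.4% (r = 0.5).
- The 9.3% needs every unfavourable assumption at once.
- The plan's projected 380 suggests that missing records would not be analysed, which favours the smaller route 2 range.
- The v = 0 range departs from the plan, because every description of the outcome uses the survey.

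The extension to Aim 3 is an inference. The stated similarity to Aim 1 is explained by covariates, not by outcome sources. On later data, the Additional Analyses text already treats screening beyond 12 months as descriptive for stool-test screenees, which makes the literal reading of the twelve-month paragraph less likely but does not remove it.

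These points lower the expected size. They do not remove the conflict.

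**Conclusion.** The concern holds. The source lists conflict in the current text, and one reading gives DSNI an outcome source that SI lacks, with no stated blinding. The direction under that reading is certain: it cannot favour SI.

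The size rests wholly on assumed capture rates and is probably small: up to about 3 points in the most unfavourable combination, against a planned 15, and nearer 1 point or less if the second pass adds little. It is zero if the 12-month review is complete and accurate, because that review covers the same months in everyone. It is also zero if the 6-month review is done identically in both arms.

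This should be fixed because it concerns the definition of the primary outcome and can be corrected cheaply. Confidence is high on the textual conflict and low on the size of any bias.

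**What to change.** 1. Define the Aim 1 and Aim 3 outcome once: the 6-month survey plus the blinded 12-month records review, with the test dated within 12 months of randomization. Use the 6-month records review for the DSNI status report only.
2. If the 6-month review is in fact done in both arms, correct the six-month paragraph instead and apply the review identically in both.
3. State in the twelve-month paragraph that last-year records on later screening are descriptive and do not enter the 12-month outcome.
4. Bring Figure 1, both procedures paragraphs, Aim 1, the RE-AIM text and the data-source table into line.
5. State whether a test recorded only in a navigator note counts at the 12-month review. Under Intervention Implementation, navigators enter test performance in DSNI charts, so chart ascertainment may still differ by arm after steps 1 to 4.

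Cost: option 1 needs wording only, and a few DSNI tests seen only at 6 months would not count. Option 2 needs about 200 extra SI chart reviews if they are not already being done.
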